## **RECRUITMENT AND CONSENT:**

### *Subject Recruitment:*

Recruited subjects will be identified through review of patients presenting for EUS for clinical care. Potential participants for the pancreatitis cohort will be reviewed to confirm diagnosis of ARP or CP by INSPIRE criteria. We are requesting a waiver of consent for chart review to confirm eligibility of the subjects for the study.

Potential participants for the control cohort will be identified by the primary investigator at the time of scheduling. These control patients will be undergoing EUS for other clinical indication. Following screening, patients will be enrolled by the research staff after informed consent is obtained through the informed consent process mentioned below. We plan to approach for enrollment, all pediatric patients that meet inclusion criteria during the funding period and anticipate no difficulty achieving our recruitment targets based on the robust referral base for our pediatric Pancreas Care Center.

### *Process of obtaining Consent (including eConsent):*

Consent, parental permission and/or assent will be obtained from all patients (pancreatitis cohort and control cohort) before any study-related procedures are performed. Written assent will be obtained from participants 11 years of age and older. The investigator will be available to answer any questions that the participant or parent may have regarding procedures, risks, and alternatives. The consent process will be documented on the informed consent progress note.

Consent may take place by several methods: in-person paper consent, in-person electronic consent (using REDCap for the eConsent) or over the phone (via paper or REDCap for eConsent). Signatures of the subject and study staff may not always occur on the same date depending on how and when the subject returns the signed consent. No matter the consenting process, study procedures will not occur prior to a fully executed consent form. Consent will be obtained following the CCHMC consenting SOP. REDCap eConsent will not replace the consenting method, it will be used as an additional resource for signing the consent form. A copy of the consent form will either be given to the subject in paper form or emailed to them via REDCap depending on how the consent is completed. In all cases, the consent process will be documented on the informed consent process note and a copy of the signed consent(s) will be kept in the patient's medical record.

Staff will make sure that the eConsent database is updated as soon as possible after a new version of the paper consent is approved. Staff will also make sure paper consents are used to consent eligible subjects in the event that the eConsent database is not updated prior to eligible subjects being available for consent approach by a member of the study staff. For the reasons described, the eConsent will not be submitted to the IRB for approval.

Subjects will be reminded that participation in research is completely voluntary. Coercion is eliminated by having the subjects sign an assent document and the parent/guardian signs the consent document. We will give potential subjects time to read the consent form, consent them in a private setting, and answer any questions they may have.

Potential subjects (or parents) will be told that the subject's (parent's) decision to participate will not affect the clinical care received.

If patients do not want to participate, at any time, they are instructed to call the Research Coordinator to opt out. The study consent process will ensure that potential subjects will be adequately informed about the study and will have an opportunity to ask questions.

#### **DATA MANAGEMENT & ANALYSIS:**

1. Data will be stored in password-protected files at CCHMC. Study data will be restricted to study personnel only after all research training is complete.
2. Once data is collected, a code will be created. The identifying information will be removed from the data file and replaced with the code. Codes will be stored in a separate file. Only research personnel will have access to the passwords and data.
3. Once the study is complete, data will be retained in a coded state for potential future currently unspecified research. Future research will require IRB approval prior to utilizing this dataset.

#### **Statistical analysis:**

*Power calculation:* Given that this is a pilot and feasibility study, a power calculation was not performed. We plan to approach for enrollment all pediatric patients that meet inclusion criteria during the funding period and anticipate no difficulty achieving our recruitment targets based on the robust referral base for our pediatric Pancreas Care Center.

*Aim1:* Frequencies will be used to describe the presence of EUS findings in patients with ARP, CP and controls. Groups will be compared using Fisher's exact and Chi-square tests as appropriate. These tests will also be used, as appropriate to compare the relationship between EUS and other imaging findings.

*Aim2:* Means, standard deviations, 95% confidence intervals will be used to describe TUS and EUS SWE results for patients with ARP, CP and for controls. Agreement between TUS and EUS SWE will be analyzed using Pearson correlations, intraclass correlation coefficients and Bland-Altman analyses. Sensitivity and specificity and 95% confidence intervals will be calculated for diagnosis of CP by SWE using INSPIRE criteria and for prediction of the presence of fibrosis on histology.

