**SPECIFIC AIMS**

The aims of the proposed study are as follows:

**Aim 1: Characterize endoscopic ultrasound (EUS) findings of pediatric acute recurrent pancreatitis (ARP) and chronic pancreatitis (CP).**

Adult criteria for EUS diagnosis of CP exist, but no such criteria exist for children. As such, the applicability of current diagnostic criteria to pediatric patients is unknown.

**1.1: Catalogue grayscale EUS findings of ARP and CP in a pediatric cohort and compare to healthy controls. Hypothesis:** EUS findings of ARP and CP in pediatric patients will differ from those of adult ARP and CP and will be characteristically different

from healthy controls. *Exp1:* We will catalogue grayscale EUS findings in 40 pediatric patients with known history of ARP or CP undergoing clinically indicated EUS and will compare those with findings in 20 patients without a history of pancreatitis who are undergoing EUS for other indications.

**1.2: Benchmark grayscale EUS against other imaging modalities for diagnosis of CP, particularly early CP, in children.** *Hypothesis:* Grayscale EUS findings will be more sensitive than other imaging modalities in all stages of CP. *Exp2:* We will test associations, in blinded fashion, of grayscale EUS findings catalogued under S.A1.1 in enrolled children with findings on alternative pancreas imaging modalities performed for clinical indications. Specifically, we will correlate to endoscopic retrograde cholangiopancreatography (ERCP), magnetic resonance cholangiopancreatography (MRCP) and computed tomography (CT) performed for clinical indications within +/- 3 months of the EUS.

**Aim 2: Define the diagnostic performance of ultrasound elastography for CP and pancreatic stiffness as a measure of fibrosis in pediatric patients.**

**2.1: Define the diagnostic performance of EUS and TUS elastography for pediatric CP.** *Hypothesis:* EUS and TUS elastography will have high specificity for CP with increased stiffness in patients compared to controls. *Exp 1:* Patients enrolled under Aim 1 will undergo shear wave elastography (SWE) measurement of the pancreas during EUS. These same patients will undergo research TUS with SWE of the pancreas. SWE results by both EUS and TUS will be evaluated for diagnostic performance for CP.

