### **STUDY PROCEDURES:**

Approximately 60 participants will be recruited to enroll in the study. Forty participants will have ARP or CP as defined by the International Study Group of Pediatric Pancreatitis: In search for a cure (INSPIRE)[18]. Twenty participants from this cohort will be undergoing TPIAT or other pancreatic resection. Another twenty participants will be controls with no history of pancreatic disease undergoing EUS for other clinical indications.

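### If sparse Aim 1 tables go to Fisher's exact test, the ARP-v-control and CP-v-control comparisons run well below 5%; Boschloo's test loses nothing against Fisher and, at some ARP/CP splits, gains power

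*Combined protocol and SAP*

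**What the plan says.** The Aim 1 paragraph of the Statistical analysis section first describes three groups: "Frequencies will be used to describe the presence of EUS findings in patients with ARP, CP and controls". It then says "Groups will be compared using Fisher's exact and Chi-square tests as appropriate". The same tests are carried over to a second use: "These tests will also be used, as appropriate to compare the relationship between EUS and other imaging findings".

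Group sizes come from elsewhere. Study Procedures gives the patients ("Forty participants will have ARP or CP as defined by the International Study Group of Pediatric Pancreatitis") and the controls ("Another twenty participants will be controls with no history of pancreatic disease undergoing EUS for other clinical indications"). Aim 1.1 in Specific Aims compares the 40 patients with the controls: the investigators "will compare those with findings in 20 patients without a history of pancreatitis".

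The documents do not give the split of the 40 into ARP and CP, the rule for choosing between the two tests, the pairs of groups to be tested, the significance level or the sidedness. There is no power target: "Given that this is a pilot and feasibility study, a power calculation was not performed".

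**The concern.** Findings that could mark disease are those seldom seen in controls. With 20 controls, such findings give small expected counts, and the usual practice is then to use Fisher's exact test. Fisher conditions on both margins of the table, whereas this design fixes only the group sizes. In small groups the test can attain only a few error rates, all well under the nominal level.

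ARP and CP are described separately, so each comparison with controls rests on fewer than 40 patients. If these comparisons are run at a true level of 1% or 2% when 5% was intended, some real differences will miss significance for no reason other than the choice of test. The study plans only 20 controls, so a test that uses the same data better is worth considering.

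**Working it through.** **Inputs.** From the documents: 40 patients, 20 controls, Fisher or chi-square. Assumed: two-sided 5%; Fisher when the smallest expected count is below 5, uncorrected chi-square otherwise; several ARP/CP splits; a range of finding rates. The plan states no power or error rate, so there is no figure to reproduce.

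**Method.** For groups of n1 and n2 with a and b findings, every table (a, b) was enumerated. The probability of rejection is the sum over rejected tables of Bin(a; n1, p1) × Bin(b; n2, p2). Size sets p1 = p2; power sets them apart. The smallest expected count is min(n1, n2) × min(s, N − s)/N, with s = a + b and N = n1 + n2. At 20 v 20, Fisher therefore applies when s or 40 − s is below 10; at 40 v 20, when s or 60 − s is below 15. Boschloo orders tables by the two-sided Fisher p-value and takes the largest cut-off whose maximum size over all common rates is at most 5%.

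**One table.** For 6/20 v 1/20, the hypergeometric probability of this table is C(20,6) × C(20,1)/C(40,7) = 775,200/18,643,560 = 0.0416. For 7 v 0 it is 77,520/18,643,560 = 0.0042. Two-sided Fisher p = 2 × (0.0416 + 0.0042), about 0.091 from unrounded terms. Boschloo p = 0.046.

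**Size of each test alone (%)**

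| Sizes | Test | Rate 5% | Rate 10% | Rate 20% | Maximum |
|---|---|---|---|---|---|
| 20 v 20 | Fisher | 0.19 | 1.18 | 2.26 | 2.5 |
| 20 v 20 | Boschloo | 0.21 | 1.68 | 4.43 | 4.6 |
| 40 v 20 | Fisher | 1.50 | 2.80 | 3.48 | 3.7 |
| 40 v 20 | Boschloo | 1.50 | 2.80 | 3.76 | 4.9 |

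**Dominance.** Fisher at 5% has unconditional size of at most 5%. Boschloo uses the same ordering, so its cut-off cannot be stricter and its rejection region contains Fisher's. Enumeration found no Fisher rejection lost at any size pair checked.

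**Power: planned rule, then Boschloo in place of Fisher (%)**

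| Patients v controls | Finding rates | Planned | Changed |
|---|---|---|---|
| 20 v 20 | 30% v 5% | 47 | 54 |
| 20 v 20 | 25% v 5% | 31 | 38 |
| 20 v 20 | 20% v 0% | 37 | 37 |
| 25 v 20 | 30% v 5% | 52 | 62 |
| 30 v 20 | 20% v 5% | 20 | 30 |
| 30 v 20 | 20% v 0% | 39 | 57 |
| 22 v 20 | 30% v 5% | 53 | 53 |
| 18 v 20 | 30% v 5% | 51 | 54 |
| 10 v 20 | 30% v 5% | 39 | 39 |
| 40 v 20 | 30% v 5% | 66 | 66 |
| 40 v 20 | 20% v 5% | 27 | 27 |

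At 40 v 20, Boschloo's 14 extra rejection tables all have at least 14 findings in 60 children, and under the assumed rule chi-square takes over at 15. That is why uncommon findings gain nothing there.

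**Two limits on the change.**

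- The form computed by scipy (twice the smaller one-sided p) does not always dominate Fisher. For 0/35 v 3/20, Fisher p = 0.043 and this form gives 0.051.
- If chi-square is kept for larger expected counts, the combined rule does not strictly hold 5%. Its maximum size is 5.3% at 20 v 20 (5.2% under the planned rule), 5.5% at 40 v 20 (5.5%), and 5.6% at 30 v 20 (5.6%) and at 15 v 20 (4.7%).

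**The case against.** The strongest reply is that the only comparison whose sizes the documents fix, "compare those with findings in 20 patients without a history of pancreatitis who are undergoing EUS for other indications" set against the 40 patients, shows no gain for uncommon findings. This stands. A reader might infer that Fisher's conservatism at these group sizes is all recoverable. It is not: at 40 v 20 and a common rate of 5%, Boschloo's own size is still 1.5%, because the sparse data cause the conservatism there.

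A second reply is that the gains elsewhere rest on an unstated split and are erratic. They are present at 20, 25 and 30 v 20 but absent at 22 and 10 v 20. This also stands, so no single range of gain can be promised.

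A third is that the Fisher fallback, the 5% level and pairwise testing are all assumed. If ARP, CP and controls are compared in one three-group test, a 2×2 Boschloo test does not apply. The fallback is the ordinary reading of the plan's wording, but it is not written there.

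Finally, Fisher's test is valid and conventional, and this is a pilot that catalogues findings. The frequencies will be reported whichever side of 0.05 a p-value falls, so it would be too strong to say that material for later pediatric criteria is lost. What survives is narrower: for two-group tables, a test exists that never does worse than Fisher and sometimes does clearly better, with no extra children.

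**Conclusion.** The point holds in a limited form. Under a two-sided 5% level and a Fisher fallback for expected counts below 5, sparse ARP-v-control and CP-v-control comparisons are run well below 5%: at most 2.5% for Fisher at 20 v 20. Boschloo's test ordered by the two-sided Fisher p-value keeps every Fisher rejection and its own size at or below 5%. In the scenarios shown, the gain over the planned rule runs from nil to about 10 points when 5% of controls have the finding, and reaches 18 points (39% to 57%) at 30 v 20 with 20% v 0%. It is nil for uncommon findings at 22 v 20, 10 v 20 and pooled 40 v 20.

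The documents do not support three stronger readings: that Fisher's test is an error here, that power is recovered at every plausible split, or that any software version of Boschloo's test dominates Fisher. The matter is optional and low in severity.

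**What to change.** In the Aim 1 paragraph of the Statistical analysis section, add: *For two-group comparisons of independent groups (ARP v controls, CP v controls, all patients v controls), Boschloo's unconditional exact test with the two-sided Fisher p-value as its statistic will replace Fisher's exact test.* State the significance level and sidedness in the same place.

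The plan should also say which of two options applies to tables with expected counts of 5 or more:

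- Keep chi-square, and note that the combined rule can slightly exceed 5% (about 5.3% to 5.6% at several splits).
- Use Boschloo for all two-group tables. This holds 5% but costs roughly 5 to 6 points of power at worst against the planned rule for common findings.

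The sentence must not be applied to a three-group test or to EUS-v-other-imaging comparisons in the same children, which are paired.

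The cost is one sentence and a check of which two-sided form the software computes; the twice-one-sided form should not be used if dominance over Fisher is claimed. The test is less familiar to readers, so Fisher p-values can be shown beside it.

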***\*irreversible structural changes:***

- *Ductal calculi, dilated side branches, parenchymal calcifications found in any imaging (abdominal ultrasound (abd US), magnetic resonance imaging/magnetic resonance cholangiopancreatography (MRI/MRCP), computerized tomography (CT), endoscopic retrograde cholangiopancreatography (ERCP), endoscopic US (EUS).*

- *Ductal obstruction or stricture/dilatation/irregularities that are persistent (for >2 months) on any imaging.*
- *Parenchymal atrophy, irregular contour, accentuated lobular architecture, cavities alone are not diagnostic findings for CP.*
- *Surgical or pancreatic biopsy specimen demonstrating histopathologic features compatible with CP (acinar atrophy, fibrosis, protein plugs, infiltration with lymphocytes, plasma cells, macrophages).*

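### Aim 1.2 claims that EUS is more sensitive than ERCP, MRCP and CT, but the planned tests measure association and no paired sensitivity comparison is specified

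*Combined protocol and SAP*

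**What the plan says.** Specific Aims, Aim 1.2, states a directional hypothesis: "Grayscale EUS findings will be more sensitive than other imaging modalities in all stages of CP". The comparators are ERCP, MRCP and "computed tomography (CT) performed for clinical indications within +/- 3 months of the EUS". Each comparison is therefore within the child, and only in children who had that other test.

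The experiment described under the same aim has a different target: "We will test associations, in blinded fashion, of grayscale EUS findings catalogued under S.A1.1 in enrolled children with findings on alternative pancreas imaging modalities".

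The Statistical analysis section, Aim 1, gives frequencies and then "Groups will be compared using Fisher's exact and Chi-square tests as appropriate". It carries those tests over to the imaging comparison: "These tests will also be used, as appropriate to compare the relationship between EUS and other imaging findings". Under Aim 2 the same section says "Sensitivity and specificity and 95% confidence intervals will be calculated for diagnosis of CP by SWE using INSPIRE criteria", and adds the same measures for fibrosis on histology. No sensitivity is planned for grayscale EUS, MRCP, CT or ERCP, and no paired method is named.

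**The concern.** Association and difference in sensitivity are separate quantities. Two modalities can agree closely and have equal sensitivity, which gives a strong association and no difference. They can also be unrelated within the child while one detects twice as many cases, which gives no association and a large difference. If the association p-value is read as evidence on Aim 1.2, it can mislead in either direction.

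The Study Design section presents this pilot as the basis for larger studies and possibly for paediatric EUS criteria. Those studies would need the sensitivity difference and its precision, and the plan produces neither.

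**Working it through.** **Inputs.** The plan states no sample size calculation, alpha or effect size, so there is no figure of its own to reproduce. Study Procedures gives 40 children with ARP or CP combined. It does not give the number with CP, or the number of those with each comparator. I assume n = 10 to 30 CP children with both tests, and two-sided 5% tests. All cell counts and sensitivities below are illustrative assumptions.

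**Notation.** Among CP children with both tests: a = both positive, b = EUS only, c = comparator only, d = neither.

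- EUS sensitivity = (a+b)/n and comparator sensitivity = (a+c)/n, so the paired difference = (b−c)/n.
- Cross-table association depends on ad − bc, with phi = (ad−bc)/√[(a+b)(c+d)(a+c)(b+d)].
- Exact McNemar tests b against c with a binomial(b+c, ½).

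**Table (a), 13/2/2/8, n=25.**

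- Sensitivities are 15/25 and 15/25, so 60% each, with difference (2−2)/25 = 0.
- phi = (13×8 − 2×2)/√(15×10×15×10) = 100/150 = 0.67.
- Cross-table Fisher p=0.002; exact McNemar p=1.0.
- The 95% CI for the difference is −17 to +17 points (Newcombe paired method with continuity-corrected phi; ±15 without that correction).

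**Table (b), 8/12/2/3, n=25.**

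- Sensitivities are 20/25 = 80% and 10/25 = 40%, with difference (12−2)/25 = 40 points (95% CI 13 to 60).
- ad − bc = 8×3 − 12×2 = 0, so phi = 0 and cross-table Fisher p=1.0.
- Exact McNemar p = 2×(1+14+91)/2^14 = 212/16384 = 0.013.

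**Rejection rates**, by exact enumeration of all tables:

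| True sensitivities, phi | Test | n=10 | 15 | 20 | 25 | 30 |
|---|---|---|---|---|---|---|
| 60% v 60%, 0.25 | cross-table Fisher | 5% | 10% | 12% | 19% | 20% |
| 60% v 60%, 0.5 | cross-table Fisher | 20% | 38% | 48% | 65% | 72% |
| 80% v 40%, 0 | cross-table Fisher | 0.6% | 1.3% | 1.6% | 1.9% | 2.4% |
| 80% v 40%, 0.25 | cross-table Fisher | 1.2% | 3.7% | 5.4% | 9.5% | 13.4% |
| 80% v 40%, 0 | exact McNemar | 20% | 44% | 62% | 75% | 84% |

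With equal 60% sensitivities, exact McNemar rejects in 2.3% of studies or fewer at every n and both values of phi.

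**The other reading: Fisher on the two proportions as if from independent groups.** This addresses the right difference but ignores the pairing.

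- It gives p=1.0 in table (a) and p=0.0086 in table (b).
- For 80% v 40% at phi 0 its power is 25/45/65/79/85% across the same n, so nothing is lost there.
- With positive within-child correlation it tends to be conservative. For 85% v 60%, n=25, phi 0.25, unpaired Fisher has 37% power and chi-square 54%, against 47% for exact McNemar and 59% for mid-p McNemar.
- For counts 28/6/0/6 (n=40, the upper limit), unpaired Fisher gives p=0.18 and exact McNemar p=0.031.

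**Small subsets.** At n=10 with 85% v 60%, exact McNemar power is 2% to 5% and mid-p 8% to 12%. No test will settle the question there, so the estimate and its interval must carry the result.

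**The case against.** The strongest reply is that the plan can be read more kindly. Comparing and benchmarking could mean comparing two proportions, and on that reading the named tests point the right way in both worked tables, at little cost in power. That is correct as far as it goes. But the stated target is association in the aims and a relationship in the analysis section. The qualifier 'as appropriate' chooses between two named tests and does not bring in a third. Even the kind reading leaves no sensitivity and no difference with an interval for Aim 1.

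A second objection is about realism. The Definitions section lets a child qualify as CP by changes such as "Ductal calculi, dilated side branches, parenchymal calcifications found in any imaging", EUS included, or by histology. That tends to empty the 'neither' cell. With d=0, ad − bc = −bc, so phi cannot be positive, and the scenarios at phi 0.25 and 0.5 fit poorly. This stands as a limit on how literally to take the false-positive rates. It does not rescue the test, because the association would then partly reflect how CP was defined. Likewise, phi 0 is the extreme case for 80% v 40%. At phi 0.25 the cross-table test does better, though it still reaches only 13.4% at n=30.

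Third, a paired sensitivity has its own weaknesses: the reference standard includes the tests compared, and the comparators were done only when clinically indicated, so the subset is selected. Both points stand and should be stated as limitations.

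Finally, this is a pilot with no decision rule attached to Aim 1.2, and the paired data will exist anyway. That limits the harm. But a difference computed later would not be prespecified, and the stated hypothesis would still have no planned analysis.

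**Conclusion.** The concern holds. Followed as written, the Aim 1.2 analysis tests association while the hypothesis is about a difference in sensitivity, and no estimate of that difference is planned. With 25 assumed CP children, the association test is significant in 65% of studies when both sensitivities are 60% and phi is 0.5. It is significant in about 2% when EUS has 80% against 40% at phi 0, where exact McNemar reaches 75%.

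These rates rest on assumed numbers, sensitivities and correlations. They show that the two questions differ and do not forecast this study's error rate. The mismatch itself follows from the text alone. The point should be fixed, but it does not affect the conduct of the study.

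**What to change.** Keep Fisher's exact and chi-square for comparing ARP, CP and controls, and for associations between individual findings. Add to the Aim 1 analysis wording such as:

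> Among children with CP who had EUS and the comparator within 3 months of each other, we will report the sensitivity of each modality and the paired difference with its 95% confidence interval, separately for MRCP, CT and ERCP. Positivity will follow the criteria in Table 1, with cut-offs fixed before analysis. An exact or mid-p McNemar test will support the estimate; the estimate and interval are the main result because subsets may be small.

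Also:

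- report how many CP children had each comparator, and state as a limitation that they were selected by clinical indication;
- state as a limitation that the CP definition counts findings from the modalities compared;
- say how CP stage is assigned, or drop the claim about all stages.

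If only association is intended, reword the Aim 1.2 hypothesis as descriptive and remove the claim of greater sensitivity.

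The cost is a few sentences and one positivity cut-off per modality. No new data or visits are needed.

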#### *Procedures and Imaging:*

EUS will be performed as part of routine clinical care using a GF-UCT180 curvilinear array ultrasound gastroscope (Olympus America Inc; Center Valley, PA). Grayscale findings (Table 1) will be recorded and documented for clinical care. Research EUS SWE measurements will be obtained using the Aloka Arietta 850 AT processor (Olympus America Inc; Center Valley, PA) with SWE measurements taken from each of the head, genu, body and tail of the pancreas. Research TUS SWE will be performed using a Canon Aplio i800 ultrasound system and a curved 1-6 MHz transducer. 2D SWE will be performed with measurement of shear wave speed in the head, body and tail of the pancreas.

Modality	Findings
EUS	Rosemont and Conventional Criteria
MRI	Atrophy T1 signal (signal intensity ratio, relaxometry) Enhancement Cambridge Criteria
CT	Atrophy Calcifications Duct dilation
ERCP	Cambridge Criteria

**Table 1:** EUS and other imaging findings to be catalogued and compared for diagnosis of CP

MRCP or CT imaging within 3 months of the EUS will be reviewed blinded to EUS and SWE findings for findings of CP (Table 1). Fluoroscopic pancreatogram images from patients with an ERCP within this time frame will be scored using Cambridge Criteria.[19]

Research EUS SWE measurements are anticipated to add approximately 5 minutes to the total procedure time. Research TUS SWE will take no more than 20 minutes and may or may not occur on the same day as the EUS procedure.

**Specimen histology:** A small core of pancreatic tissue is routinely collected from all patients undergoing TPIAT at our institution and a similar sample would be obtained from patients undergoing other resections. Findings from enrolled participants' samples will be reviewed for the presence of fibrosis using a four-stage scoring system adopted by Wellner et al.

Data collected from Epic may include: patient age, sex, height/ weight, relevant lab values, results of imaging modalities (MRCP, CT, US, or ERCP, EUS), relevant genetic testing results, pancreatic function testing results, medications, hospital stay, complications, clinical course, interventions/surgical procedures, and other relevant clinical data.

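### Aim 1 relates EUS to other imaging only by Fisher's exact and chi-square tests, which need an unstated cut-point for continuous MRI T1 and ignore the order of Cambridge grades

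*Combined protocol and SAP*

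**What the plan says.** Under Statistical analysis, Aim 1, the plan describes the presence of EUS findings by frequencies and compares ARP, CP and control groups by Fisher's exact and chi-square tests. It continues: "These tests will also be used, as appropriate to compare the relationship between EUS and other imaging findings". No other method is named for Aim 1.

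Table 1 (Procedures and Imaging) sets out what will be compared. For MRI it includes "T1 signal (signal intensity ratio, relaxometry" and the Cambridge criteria. ERCP pancreatograms "will be scored using Cambridge Criteria". Other entries, such as calcifications and duct dilation on CT, can be read as present or absent.

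Specific Aims, Aim 1.2, says that EUS findings will be correlated with ERCP, MRCP and CT, and names no method. Methods for continuous data (Pearson and intraclass correlation, Bland-Altman) appear only under Aim 2, for elastography. On size the plan says "Given that this is a pilot and feasibility study, a power calculation was not performed".

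**The concern.** The tests named do not match the data to be collected. A T1 ratio or relaxation time has no place in a contingency table until someone cuts it, and the documents give no threshold. Whoever runs the analysis must pick one, probably with the data in hand. Cambridge grades fit in a larger table, but Fisher's exact and the ordinary chi-square test give the same answer whichever way the grades are arranged, so a steady rise in severity counts no more than a haphazard pattern.

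Aim 1.2 is the benchmarking aim, with emphasis on early CP, where changes are likely to be graded. Study Design says the results may serve as preliminary data for paediatric EUS criteria. A cut-point found in this sample could therefore carry into later work. Only scans done for clinical reasons near the time of EUS count, so the MRI subset may be smaller than the enrolled sample and can ill afford the loss of information.

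**Working it through.** **Step 1. Set the data beside the tests.**

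| Item in Table 1 | Scale | Can it enter Fisher or chi-square? | What is lost |
|---|---|---|---|
| T1 intensity ratio, T1 relaxometry | continuous | only after a cut, none stated | information; the threshold is left to the analyst |
| Cambridge grade (MRI, ERCP) | ordered | yes, uncut, in an r × c table | the ordering |
| Calcifications, duct dilation (CT) | present/absent if so recorded | yes | nothing |

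**Step 2. Inputs for an illustration.** The plan has no power figure to reproduce.

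- From the documents: "Forty participants will have ARP or CP" and "Another twenty participants will be controls with no history of pancreatic disease undergoing EUS for other clinical indications", so 60 in all. Comparison scans are those "performed for clinical indications within +/- 3 months of the EUS"; how many children will have an MRI is not given.
- Assumed: 24, 30 or 40 children with MRI; latent correlation ρ of 0.4 or 0.5 between T1 and the EUS severity underlying a finding; two-sided 5% level; the EUS finding present in half the children.

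**Step 3. Large-sample guide.** For normal data and a small shift, splitting one variable at its median keeps 2/π = 0.64 of the effective sample size, a loss of 36%. A direct calculation agrees. For a standardised difference d = 0.8 and 80% power:

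- T1 whole: n per group = 2(1.960 + 0.842)²/0.8² = 24.5, so 25.
- T1 cut midway: the proportions above the cut are Φ(0.4) = 0.655 and 0.345, and n per group = [1.960√(2 × 0.25) + 0.842√(2 × 0.655 × 0.345)]²/0.311² = 39.4, so 40.
- Ratio 25/40 = 0.63.

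**Step 4. Simulation at the assumed sizes.** Bivariate normal pairs with correlation ρ were drawn and the EUS variable was made binary at its median. T1 was then tested whole (Mann-Whitney) or after its own median split (Fisher).

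| n with MRI | ρ | T1 whole | T1 split | Relative loss |
|---|---|---|---|---|
| 24 | 0.5 | 48% | 34% | 14/48 = 29% |
| 40 | 0.5 | 73% | 45% | 28/73 = 38% |
| 30 | 0.4 | 39% | 22% | 17/39 = 44% |

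Repeat runs move these figures by a few percentage points.

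**Step 5. How far Fisher's conservatism contributes.** With exact halves on both margins the possible tables are few, and the attained level is the Fisher p-value of the least extreme table that rejects:

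- n = 24: 9/3 against 3/9, p = 0.039.
- n = 30: 11/4 against 4/11, p = 0.027.
- n = 40: 14/6 against 6/14, p = 0.026.

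The split test therefore works below the nominal 5%, while Mann-Whitney runs close to it. Part of the gap in Step 4 comes from this and not from the cut itself.

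**Step 6. Sensitivity to the assumptions.** With a binary EUS finding (prevalence 30% or 50%), d from 0.6 to 1.2 and n from 20 to 40, Fisher after a median split keeps between 0.26 and 0.80 of the t-test's power. At n = 60 it keeps 0.50 to 0.92. Uncorrected chi-square sometimes keeps more, partly through a looser type I error when groups are small and unequal.

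**The case against.** The best defence is that the wording is incomplete and is not a decision to dichotomise. Nowhere do the documents say T1 will be cut, and Aim 1.2 speaks of correlating findings. On that view the qualifier in the analysis sentence limits the categorical tests to categorical findings. This has some force, but it leaves T1 with no method at all. The qualifier most naturally chooses between the two tests just named, and Aim 2 shows that continuous-data methods are named where they are intended. Either way the text needs completing.

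It is also fair that Aim 1.2's hypothesis concerns sensitivity, which needs a positive or negative call for each modality. Some categorising is inherent there, and a rank correlation does not answer that question. A T1 threshold used for that purpose would still have to be stated beforehand.

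Two stronger readings should be resisted:

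- A reader might infer that the graded scores are also forced into cut-points. They are not: both tests accept every Cambridge grade, and only the ordering is lost.
- A reader might infer that about half the power is lost. That figure comes from splitting both variables; at n = 40 and ρ = 0.5, for example, Pearson's 92% falls to 45%. The analysis section already treats EUS findings as present or absent, so the tests force a split on T1 alone.

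**Conclusion.** The point stands as a gap between the measures collected and the tests named. T1 needs a cut-point that the plan does not give, and Cambridge grades lose their order. This rests on the text and needs no power figure.

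The size is illustrative. Under the stated assumptions (24 to 40 children with MRI, latent correlation 0.4 to 0.5, prevalence one half) cutting T1 takes away roughly 30% to 45% of the power relative to keeping it whole. The documents supply none of these inputs, other reasonable settings give smaller or larger losses, and part of the loss is Fisher's conservatism.

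It would be wrong to infer that the study misses a power target, since it is a pilot and "a power calculation was not performed". The consequence is lost information and data-driven thresholds. The change should be made, but the study does not fail without it.

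**What to change.** Add to Statistical analysis, Aim 1, text to this effect:

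> T1 signal intensity ratio and T1 relaxation time will be analysed uncut, by Wilcoxon rank-sum test according to presence of an EUS finding and by Spearman correlation with 95% confidence interval against the number of EUS criteria present. Cambridge grade will be analysed as an ordered score (rank or trend test, Spearman or Kendall tau-b). Fisher's exact and chi-square tests are kept for present/absent findings. These analyses are exploratory, without multiplicity adjustment.

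This supplies the method that Aim 1.2 lacks. It needs no new data. The cost is a short SAP edit, slightly more analysis work and more exploratory tests, which is why the exploratory label belongs in the text.
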